**Table 14.3.4.1.1.1**  
**Vital Signs**  
**Safety Population**

Vital Sign	Target Visit	AD (N= )	bvFTD (N= )	All Subjects (N= )
Systolic BP (mmHg)	Baseline			
	n	n	n	n
	Mean (SD)	xx.x (xx.xx)	xx.x (xx.xx)	xx.x (xx.xx)
	Median	xx.x	xx.x	xx.x
	Min, Max	xx, xx	xx, xx	xx, xx
	Baseline 			
	...			
	Week 2			
	...			
	Change from Baseline to Week 2			
...				

 Baseline is defined as the last non-missing value prior to first dose of study drug.

path\t\_program.sas date time

*Programming note: Table will include the following vital signs: systolic BP (mmHg), diastolic BP (mmHg), heart rate (bpm), oral temperature (°C), respiratory rate (bpm) and weight (kg) for all target visits and for Last Available On-Treatment Value. Please see Appendix A for target visits and visit windows.*

*Programming Note: Repeat table for Table 14.3.4.1.1.2 Vital Signs – Non-AChEI/Memantine Users (Safety Population)*

**Table 14.3.4.1.2.1**  
**Weight Directional Changes**  
**Safety Population**

Direction of Change	Target Visit	Category	AD (N= )	bvFTD (N= )	All Subjects (N= )
Increase	Baseline	0-5 kg	n (%)	n (%)	n (%)
		>5 – 10 kg	n (%)	n (%)	n (%)
		>10 – 15 kg	n (%)	n (%)	n (%)
		etc...			
Decrease	Baseline	0-5 kg	n (%)	n (%)	n (%)
		>5 – 10 kg	n (%)	n (%)	n (%)
		>10 – 15 kg	n (%)	n (%)	n (%)
		etc...			
	etc...	etc...			

path\t\_program.sas date time

*Programming note: Table will include all target visits and Last Available On-Treatment Value. Please see Appendix A for target visits and visit windows..*

*Programming Note: Repeat table for Table 14.3.4.1.2.2 Weight Directional Changes – Non-AChEI/Memantine Users (Safety Population)*

**Table 14.3.4.1.3.1**  
**Incidence of Potentially Clinically Significant Vital Sign Results**  
**Safety Population**

Any Post-Baseline Clinically Significant Abnormalities?	Potentially Clinically Significant Criteria	Target Visit	AD (N= )	bvFTD (N= )	All Subjects (N= )
Systolic Blood Pressure	Criteria	Baseline	n (%)	n (%)	n (%)
		Any Post-Baseline Visit	n (%)	n (%)	n (%)
		Day 1 Post-Dose	n (%)	n (%)	n (%)
		Week 2	n (%)	n (%)	n (%)
Diastolic Blood Pressure	Criteria	Baseline	n (%)	n (%)	n (%)
		Any Post-Baseline Visit	n (%)	n (%)	n (%)
		Day 1 Post-Dose	n (%)	n (%)	n (%)
		Week 2	n (%)	n (%)	n (%)

path\t\_program.sas date time

*Programming note: Table will include all parameters ( systolic BP (mmHg), diastolic BP (mmHg), pulse (bpm), temperature (°C), and weight (kg)) with defined potentially clinically significant ranges at each post-Baseline visit. Table will include all target visits and Last Available On-Treatment Value. Please see Appendix A for target visits and visit windows*

*Programming Note: Repeat table for Table 14.3.4.1.3.2 Incidence of Potentially Clinically Significant Vital Sign Results – Non-AChEI/Memantine Users (Safety Population)*

**Table 14.3.4.2**  
**Physical Examination by Visit**  
**Safety Population**

Body System	Time Point	AD (N= )	bvFTD (N= )	All Subjects (N= )
Skin	Baseline 	(n= )	(n= )	(n= )
	Normal	n (%)	n (%)	n (%)
	Abnormal NCS	n (%)	n (%)	n (%)
	Abnormal CS	n (%)	n (%)	n (%)
	Week 2	(n= )	(n= )	(n= )
	Normal	n (%)	n (%)	n (%)
	Abnormal NCS	n (%)	n (%)	n (%)
	Abnormal CS	n (%)	n (%)	n (%)
	...			
Head				
...				

Note: NCS = Not clinically significant, CS = Clinically significant.

 Baseline is defined as the last non-missing value prior to first dose of study drug.

path\t\_program.sas date time

*Programming note: Table will include all body systems for all target visits and for Last Available On-Treatment Value. Please see Appendix A for target visits and visit windows.*

**Table 14.3.4.3**  
**Neurological Examination by Visit**  
**Safety Population**

Body System	Time Point	AD (N= )	bvFTD (N= )	All Subjects (N= )
Appearance	Baseline 	(n= )	(n= )	(n= )
	Normal	n (%)	n (%)	n (%)
	Abnormal NCS	n (%)	n (%)	n (%)
	Abnormal CS	n (%)	n (%)	n (%)
	Week 2	(n= )	(n= )	(n= )
	Normal	n (%)	n (%)	n (%)
	Abnormal NCS	n (%)	n (%)	n (%)
	Abnormal CS	n (%)	n (%)	n (%)
	...			
	Behaviour			
...				

Note: NCS = Not clinically significant, CS = Clinically significant.

 Baseline is defined as the last non-missing value prior to first dose of study drug.

path\t\_program.sas date time

*Programming note: Table will include all body systems for all target visits and for Last Available On-Treatment Value. Please see Appendix A for target visits and visit windows.*

**Table 14.3.4.4.1**  
**Serotonin Toxicity (Syndrome) Assessment by Visit**  
**Safety Population**

	Time point	AD (N= )	bvFTD (N= )	All Subjects (N= )
Sign or Symptom of Serotonin Toxicity (Syndrome) Exhibited 	Baseline	(n= ) n (%)	(n= ) n (%)	(n= ) n (%)
	Week 2	(n= ) n (%)	(n= ) n (%)	(n= ) n (%)
	...			

Note: Baseline is defined as the last non-missing value prior to first dose of study drug.

 Subjects are counted if they answered “yes” to any of the signs or symptoms on the Serotonin Toxicity (Syndrome) Assessment form.

path\t\_program.sas date time

*Programming note: Table will include all target visits and Last Available On-Treatment Value. Please see Appendix A for target visits and visit windows.*

*Programming Note: Repeat table for Table 14.3.4.4.2 Serotonin Toxicity (Syndrome) Assessment by Visit – Non-AChEI/Memantine Users (Safety Population)*

**Table 14.3.4.5.1  
Central ECG Data by Visit  
Safety Population**

ECG Parameter	Time Point	AD (N= )	bvFTD (N= )	All Subjects (N= )
Ventricular Rate (bpm)	Baseline 			
	N	n	n	n
	Mean (SD)	xx.x (xx.xx)	xx.x (xx.xx)	xx.x (xx.xx)
	Median	xx.x	xx.x	xx.x
	Min, Max	xx, xx	xx, xx	xx, xx
	Week 26			
	N	n	n	n
	Mean (SD)	xx.x (xx.xx)	xx.x (xx.xx)	xx.x (xx.xx)
	Median	xx.x	xx.x	xx.x
	Min, Max	xx, xx	xx, xx	xx, xx
	Change from Baseline to Week 26			
	N	n	n	n
	Mean (SD)	xx.x (xx.xx)	xx.x (xx.xx)	xx.x (xx.xx)
	Median	xx.x	xx.x	xx.x
	Min, Max	xx, xx	xx, xx	xx, xx
...				
PR Interval (msec)				
...				

 Baseline is defined as the mean of the last non-missing triplicate values prior to first dose of study drug.  
Note: The summaries are based on the measurements from central read (BIOCLINICA).

path\t\_program.sas date time

*Programming note: table will include all target visits and Last Available On-Treatment Value and the following ECG parameters: Ventricular Rate (beats/min), PR Interval (msec), QRS Duration (msec), QTcB Interval (msec), QTcF Interval (msec). See Appendix A for visit windows.*

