Should serotonin syndrome (toxicity) be suspected clinically, “serotonin toxicity” should be recorded as the adverse event rather than the individual signs or symptoms. These should be indicated by answering “yes” or “no” to each of the signs and/or symptoms indicated on the form provided in the eCRF. These signs and symptoms, based on physical and neurological examination, include the following: abnormal conscious level (delirium), agitation or akathisia, elevated mood, insomnia, myoclonus, tremor, mydriasis, nystagmus, clonus, hyperreflexia, hypertonia (rigidity), dizziness, incoordination, shivering, diaphoresis (sweating), diarrhea, pyrexia (fever), tachycardia, tachypnea or dyspnea, hypertension or hypotension. An “other” field should also be included in the eCRF to indicate any additional findings.

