9.6.4 Electrocardiogram

ECG results will be provided by the central ECG reader. Tabular summaries and analyses are to be based on the central ECG data. Machine-read ECG results and interpretations are to be recorded in the eCRF and included in a separate listing; this also applies to any subsequent local interpretations if used to make dosing or patient management decisions.

ECG interval data will be summarized based on the average of the triplicate measures. All other study visit ECG data (interpretations or means of triplicate measurements if

performed for clinical reasons) will be summarized separately. ECG interval and ventricular rate data will be summarized using descriptive statistics for both the original values and the change from Baseline. Windows for each target visit will be used (additional details provided in the SAP). Parameters to be analyzed include heart rate (HR) and PR, QRS, QT, and corrected QT (using Fridericia's and Bazett's corrections), and RR intervals. Counts and percent of subjects in each result category will be tabulated. Overall interpretations of abnormality(ies) will also be tabulated, with subjects categorized by whether or not they have treatment-emergent abnormalities.

Subjects are also to be categorized and enumerated on the basis of QTc interval and change from Baseline as follows:

- QTcB/F outliers (in categories of > 450 to ≤ 480 , > 480 to ≤ 500 , > 500 msec)
- Change in QTcB/F outliers (in categories of > 30 to ≤ 60 , > 60 to < 90 , ≥ 90 msec)

All HR, interval data, and interpretations will be listed. Any new finding after Baseline will be categorized into diagnostic groups: rhythm, conduction, hypertrophy, arrhythmia, ischemia, infarction, other.

9.6.5 *Physical and Neurological Examinations and Serotonin Syndrome (Toxicity)*

Physical and neurological examination results obtained at Baseline (Visit 1) will be summarized by body system. Evaluation at subsequent visits will be summarized in a treatment-emergent fashion. Summaries will present the number and percentage of subjects with normal and abnormal observations by body system/parameter evaluated. By-subject listings will detail the abnormality(ies). Ratings for signs and symptoms of serotonin syndrome (toxicity) will also be summarized. For each target visit, the number of subjects for whom "yes" is answered for any of the signs and/or symptoms will be tabulated. A by-subject listing of results will also be prepared.

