#### **7.4 Physical and Neurological Examinations and Serotonin Syndrome (Toxicity)**

Targeted examinations were optional prior to protocol version 3.0. With version 3.0 or higher, they are to be performed at every visit (or upon early termination), including the 4-week post-treatment follow-up visit if applicable.

The targeted examinations will be focused on, but not limited to, evaluating subjects for potential serotonin toxicity and also as clinically indicated. At a minimum, they are to include assessments for serotonin toxicity, evaluation of deep tendon reflexes, clonus, and muscle rigidity; size and reactivity of pupils; dryness of oral mucosa; intensity of bowel sounds; skin color; and presence or absence of diaphoresis.

Summaries will present the number and percentage of subjects with normal and abnormal observations by body system/parameter evaluated. By-subject listings will detail any abnormalities.

Ratings for signs and symptoms of serotonin syndrome (toxicity), inclusive of the MMSE, were introduced in protocol version 3.0 and will be performed at each visit. A by-subject listing of all responses will be prepared. A separate listing will be provided for the Mini-Mental State Examination (MMSE) scores.

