14.3.4.4.2	Serotonin Toxicity (Syndrome) Ratings by Visit – Non-AChEI/Memantine Users (Safety Population)
14.3.4.5.1	Central ECG Data by Visit (Safety Population)
14.3.4.5.2	Central ECG Data – Change from Baseline in Investigator’s Overall Interpretation of Clinical Significance by Visit (Safety Population)
14.3.4.5.3	Central ECG Data – QTc Abnormalities (Safety Population)

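### The serotonin toxicity form is tabulated only as a count of subjects with any of 20 signs per visit, so a change in a specific sign cannot be identified from the tables of that form

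*SAP*

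**What the plan says.** Protocol Section 9.6.5 states: "Ratings for signs and symptoms of serotonin syndrome (toxicity) will also be summarized". It then says how: for each target visit, the number of subjects for whom a yes "is answered for any of the signs and/or symptoms will be tabulated", together with a by-subject listing.

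SAP Section 7.4 says that the ratings "were introduced in protocol version 3.0 and will be performed at each visit". For output, the section promises a listing of the form: "A by-subject listing of all responses will be prepared". The table itself is defined in Appendix G. The shell of Table 14.3.4.4.1 has one row per time point, and its footnote counts a subject who said yes "to any of the signs or symptoms on the Serotonin Toxicity (Syndrome) Assessment form". Table 14.3.4.4.2 repeats that layout for subjects not taking an AChEI or memantine.

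The items on the form are given in Protocol Section 7.1.3.2. They are "abnormal conscious level (delirium), agitation or akathisia, elevated mood, insomnia", followed by "myoclonus, tremor, mydriasis, nystagmus, clonus, hyperreflexia, hypertonia (rigidity), dizziness, incoordination, shivering, diaphoresis (sweating), diarrhea, pyrexia (fever), tachycardia, tachypnea or dyspnea, hypertension or hypotension", with an additional field for other findings.

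SAP Section 7.4 also plans a summary of the targeted physical and neurological examinations as normal or abnormal, by body system or parameter (Tables 14.3.4.2 and 14.3.4.3).

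**The concern.** Protocol Section 7.1.3 names two adverse events of special interest: hemolytic anemia and serotonin syndrome. For the second, the form is the systematic data source, yet its tabulation merges signs of very different specificity. Agitation, insomnia, dizziness, diarrhea and abnormal blood pressure are plausible in this population whatever the drug does. Clonus, hyperreflexia and mydriasis are more specific.

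Two features of the row limit what it can show.

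- It is a union of 20 items. If the common items already put many subjects in the count, a rise in a rare item adds only those subjects who were not counted already.
- It records status at the visit, not onset. A subject with insomnia at Baseline who later loses it and develops clonus is counted at both visits, and the row does not move.

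At stake is whether the clinical study report can describe which signs appeared on treatment, and in how many subjects, without someone working through a by-subject listing.

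**Working it through.** The documents give no figure to reproduce. Protocol Section 9.2 calls sample size not applicable, Section 9.3.2 plans no inferential statistics, and neither document states a background frequency for any sign. The rates below are assumptions.

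**1. Number of signs.** Listing 16.2.9.6 has 7 autonomic, 9 neuromuscular and 4 mental-state columns: 7 + 9 + 4 = 20, plus additional findings. The list in Protocol Section 7.1.3.2 also gives 20.

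**2. Size of the composite.** Assume that each sign has background prevalence p and that signs are independent. Then P(any) = 1 − (1 − p)^20.

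| p per sign | P(any of 20) |
|---|---|
| 1% | 1 − 0.99^20 = 18.2% |
| 2% | 1 − 0.98^20 = 33.2% |
| 3% | 1 − 0.97^20 = 45.6% |
| 5% | 1 − 0.95^20 = 64.2% |

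**3. Doubling one sign.** At p = 2%, let one sign go from 2% to 4%. The change in the composite is 0.98^19 × (0.98 − 0.96) = 0.681 × 0.02 = 0.0136, or about 1.4 points on a base of 33%.

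**4. A larger rise in a rarer sign.** Let one sign go from 0.5% to 2%, and let B be the rate of any other sign. The composite changes by (1 − B) × (0.02 − 0.005). Take N = 1050, the lower projection in Protocol Section 4.2, which supposes that all eligible subjects enroll. The standard error of the difference treats the two time points as independent samples. That ignores within-subject pairing, so it is only a yardstick for visibility.

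| Row | Change (points) | SE of difference (points) |
|---|---|---|
| The sign alone: 0.5% to 2%, about 5 versus 21 subjects | 1.5 | 0.48 |
| Composite, B = 5% | 1.4 | 1.05 |
| Composite, B = 20% | 1.2 | 1.78 |
| Composite, B = 40% | 0.9 | 2.14 |
| Composite, B = 60% | 0.6 | 2.13 |

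The first standard error is √[(0.005 × 0.995 + 0.02 × 0.98)/1050] = 0.0048. The per-sign change is about three times its standard error. The composite change is between about 1.4 and 0.3 times.

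**5. Where else the individual signs appear.**

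- *Listing 16.2.9.6* has every sign by subject and visit. With the form complete at Visits 1 to 6, that is up to 1050 × 6 × 20 = 126,000 responses, or 168,000 with 1400 subjects. The real number will be lower, because the form began only with protocol version 3.0.
- *Tables 14.3.4.2 and 14.3.4.3*: the examination covers reflexes, clonus, rigidity, pupils and diaphoresis, and SAP Section 7.4 promises rows by system or parameter. The shells show only Skin, Head, Appearance and Behaviour as examples, so separate reflex and clonus rows are implied but not confirmed. The categories are normal, abnormal not clinically significant and abnormal clinically significant. They have no direction, so increased and reduced reflexes are not separated.
- *AESI tables (14.3.2.14 series)*: Protocol Section 7.1.3.2 has a suspected case recorded under one event term in place of its signs, so these tables do not recover the signs.
- *Vital-sign tables* give measured temperature, pulse, respiratory rate and blood pressure. These are counterparts of some autonomic items, not the ratings.

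**The case against.** The strongest reply is that the SAP does what the protocol asks. The sentence in Protocol Section 9.6.5 saying that ratings will be summarized is followed at once by the any-sign count and the listing, and the natural reading is that these define the summary. A reader might infer that the SAP breaks a separate promise of per-sign tables; the text does not support that. Counting any sign also matches Protocol Table 7-1, which groups the signs under any one of them.

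A reader might also infer that a rise in clonus or hyperreflexia would go unseen. That is too strong, given Listing 16.2.9.6 and the examination tables.

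A third tempting reading is that the composite is swamped by complaints common in dementia. No document gives a rate for any sign, and uniform, independent prevalences are a convenience. The background also depends on when the form is used. SAP Section 7.4 says at each visit, but Protocol Section 7.1.3.2 introduces the yes/no form in the context of clinical suspicion. On that second reading incidental complaints would seldom enter the count. The composite would not be more informative, though: SAP Section 4.1 generally excludes missing values from by-visit denominators, so the row could approach 100% of completed forms.

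Finally, the study is uncontrolled and descriptive, so per-sign counts would not establish or exclude a drug effect either. That stands. They would, however, describe what appeared on treatment, which the present row does not.

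**Conclusion.** The point holds as a reporting gap. The serotonin form is tabulated only through one any-sign count per visit, with one subgroup repeat, and that count neither separates the 20 signs nor isolates new onset. A change in a specific sign cannot be identified from Tables 14.3.4.4.1 and 14.3.4.4.2. The ratings themselves are otherwise only in Listing 16.2.9.6. Some of the same findings should be in Tables 14.3.4.2 and 14.3.4.3, without direction.

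The structure of the tables is read directly from the SAP. The size of the dilution rests on assumed rates and independence. On those assumptions the composite lies between 18% and 64% for 1% to 5% per sign, and a doubling of one sign from 2% moves it by about 1.4 points. No data are lost and no protocol instruction is breached. The matter is minor, but the improvement bears on the study's long-term safety objective and costs little.

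**What to change.** In Tables 14.3.4.4.1 and 14.3.4.4.2:

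- Keep the protocol-specified any-sign row.
- Add one row per sign at each target visit, with the number of completed forms as denominator.
- Add, for each sign, the number of subjects with it absent at Baseline and present at any on-treatment visit. Limit the denominator to subjects with a Baseline rating, and state how many have none. This restriction is needed because the form began with version 3.0 (24 March 2016), while the first protocol version dates from 2014, so earlier entrants may have no Baseline rating.

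Confirm in the SAP that Table 14.3.4.3 will have separate rows for deep tendon reflexes and clonus. State also whether the form is completed at every visit or only on suspicion, since the denominators depend on it.

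The cost is extra rows in two existing shells and one derived new-onset flag per sign. It needs no new data collection and no protocol amendment.

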**Table 14.3.4.5.2**  
**Central ECG Data – Change from Baseline in Investigator’s Overall Interpretation of Clinical Significance by Visit**  
**Safety Population**

Target Visit	AD (N= ) Baseline 			bvFTD (N= ) Baseline 				All Subjects (N= ) Baseline 	
	Normal	Abnormal CS	Abnormal NCS	Normal	Abnormal CS	Abnormal NCS	Normal	Abnormal CS	Abnormal NCS
Week 26	(n=)	(n=)	(n=)	(n=)	(n=)	(n=)	(n=)	(n=)	(n=)
Normal	n (%)	n (%)	n (%)	n (%)	n (%)	n (%)	n (%)	n (%)	n (%)
Abnormal NCS	n (%)	n (%)	n (%)	n (%)	n (%)	n (%)	n (%)	n (%)	n (%)
Abnormal CS	n (%)	n (%)	n (%)	n (%)	n (%)	n (%)	n (%)	n (%)	n (%)
Week 52	(n=)	(n=)	(n=)	(n=)	(n=)	(n=)	(n=)	(n=)	(n=)
Normal	n (%)	n (%)	n (%)	n (%)	n (%)	n (%)	n (%)	n (%)	n (%)
Abnormal NCS	n (%)	n (%)	n (%)	n (%)	n (%)	n (%)	n (%)	n (%)	n (%)
Abnormal CS	n (%)	n (%)	n (%)	n (%)	n (%)	n (%)	n (%)	n (%)	n (%)
...									

Note: CS = Clinically Significant, NCS = Not Clinically Significant. The clinical significance was determined by the investigator.

Baseline is defined as the last non-missing value among triplicate values prior to first dose of study drug.

path\t\_program.sas date      time

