9.2 Sample Size Calculations

Not applicable to this open-label extension study.

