#### **7.5 Electrocardiography**

A 12-lead ECG (triplicate recording) was introduced in protocol version 3.0. Measurements are taken approximately every 6 months thereafter (or upon early termination), including the 4-week post-treatment follow-up visit if applicable. Recordings will be evaluated by a centralized ECG reading facility. Interval data (including QT and corrected QT intervals), ventricular rate, and overall interpretation are to be reported for every ECG. The interval data and ventricular rate are to be noted in the CRF as averages of the three readings (with the exception of values that are not evaluable and reported as zero, in which case the average will exclude this zero value and note in the CRF the average of values > 0).

ECG interval and ventricular rate data will be summarized using descriptive statistics. Windows for each target visit will be used ([Appendix A](#)). Parameters to be analyzed include heart rate (HR) and PR, QRS, QT, and corrected QT (using Fridericia's and Bazett's corrections), and RR intervals. Counts and percent of subjects in each result

category will be tabulated. Overall interpretations of abnormalities will also be tabulated, with subjects categorized by whether or not they have study-emergent abnormalities.

Subjects are also to be categorized and enumerated on the basis of QTcB/F interval as follows:

- Absolute measurements (in categories of  $> 450$  to  $\leq 480$ ,  $> 480$  to  $\leq 500$ ,  $> 500$  msec)
- Change from first 020 measurement (in categories of  $> 30$  to  $\leq 60$ ,  $> 60$  to  $< 90$ ,  $\geq 90$  msec)

All HR, interval data, and interpretations will be listed. Any local ECG results (optional prior to version 3.0 of the protocol) will be listed separately.

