**Listing 16.2.9.8.1**  
**Central Electrocardiogram**  
**Safety Population**

Subject ID	Visit	Assessment		Assessment Time	Heart Rate (bpm)	PR Interval (ms)	RR Interval (ms)	QRS Interval (ms)	QT Interval (ms)	QTc Interval (Fridericia) (ms)	QTc Interval (Bazett) (ms)	If Abnormal, Describe 	Any Findings Abnormal? 
		Date (Study Day)	Measurement										
xxxxxx	Screening Week 26	date9. (xx)	1st Reading	time5.	xxx	xxx	xxx	xxx	xxx	xxx	xxx		Yes: CS/NCS / No
		date9. (xx)	1st Reading	time5.	xxx	xxx	xxx	xxx	xxx	xxx	xxx		Yes: CS/NCS / No
			2nd Reading	time5.	xxx	xxx	xxx	xxx	xxx	xxx	xxx		Yes: CS/NCS / No
			3rd Reading	time5.	xxx	xxx	xxx	xxx	xxx	xxx	xxx		Yes: CS/NCS / No
			Average 		xxx	xxx	xxx	xxx	xxx	xxx	xxx		Yes: CS/NCS / No
	Week 52	date9. (xx)	1st Reading	time5.	xxx	xxx	xxx	xxx	xxx	xxx	xxx		Yes: CS/NCS / No
			2nd Reading	time5.	xxx	xxx	xxx	xxx	xxx	xxx	xxx		Yes: CS/NCS / No
			3rd Reading	time5.	xxx	xxx	xxx	xxx	xxx	xxx	xxx		Yes: CS/NCS / No
			Average 		xxx	xxx	xxx	xxx	xxx	xxx	xxx		Yes: CS/NCS / No
		...											
xxxxxx	Screening	date9. (xx)	1st Reading	time5.	xxx	xxx	xxx	xxx	xxx	xxx		Yes: CS/NCS / No	
	...												

Note: Study day is calculated as days since the date of first dose of study drug.

 Average of triplicate (or available) measurements within a visit.

 As reported by the investigator on the ECG central read CRF.

 Investigator interpretation of ECG and clinical significance

path\l\_program.sas date time

*Programming note: Sort by subject ID. Display the CRF visit label.*

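### Overall ECG interpretation is reported only as the investigator's, although the protocol bases ECG tables on the central reading, and the protocol's diagnostic groups for new findings are missing from the SAP

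*SAP*

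**What the plan says.** Protocol 7.5 sends recordings to a central reading facility and has intervals, ventricular rate and an overall interpretation reported for every ECG. Protocol 9.6.4 then sets the basis for reporting: "ECG results will be provided by the central ECG reader", and "Tabular summaries and analyses are to be based on the central ECG data". Machine-read results, and local interpretations used for dosing or management decisions, go to a separate listing. Overall interpretations are to be tabulated by treatment-emergent status, and "Any new finding after Baseline will be categorized into diagnostic groups: rhythm, conduction, hypertrophy, arrhythmia, ischemia, infarction, other".

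SAP 7.5 repeats the central evaluation and commits to this: "Overall interpretations of abnormalities will also be tabulated, with subjects categorized by whether or not they have study-emergent abnormalities". It also says that interpretations will be listed. It does not say whose interpretation is meant, and it does not carry over the diagnostic groups.

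The SAP shells are more specific. Table 14.3.4.5.2 is headed as central ECG data, but its title and footnote make it the investigator's overall interpretation: "The clinical significance was determined by the investigator". In Listing 16.2.9.8.1, the central ECG listing, the column describing an abnormality is footnoted "As reported by the investigator on the ECG central read CRF". The column recording whether any finding was abnormal is footnoted "Investigator interpretation of ECG and clinical significance".

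SAP Section 9 lists no change from the protocol and defers any to the study report.

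**The concern.** Long-term safety is a primary objective (Protocol Section 3), and protocol version 3.0 extended scheduled triplicate ECGs to all subjects. The protocol's design for these data is one standardised reader feeding the tables, with new findings grouped by kind. In the SAP, the qualitative half of the ECG (normal or abnormal, and what the abnormality is) is attributed to investigators at about 170 sites, and the grouping is absent.

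At stake is whether the report can state how many subjects developed a new ECG abnormality on treatment, and of what kind, on the basis the protocol chose.

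**Working it through.** No arithmetic formula applies. The protocol gives no sample size (Protocol 9.2: "Not applicable to this open-label extension study"), and no stated figure is in question. The check sets each ECG output against Protocol 9.6.4.

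**Step 1: source of each output.** SAP Appendix F lists three ECG tables and two ECG listings.

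- Table 14.3.4.5.1: ventricular rate, PR, QRS, QTcB and QTcF; footnoted to the central read.
- Table 14.3.4.5.2: overall interpretation as Normal / Abnormal NCS / Abnormal CS; the investigator's.
- Table 14.3.4.5.3: QTcF and QTcB categories, absolute and change; footnoted to the central read.
- Listing 16.2.9.8.1 (central): intervals for each reading and their average; both abnormality columns attributed to the investigator; no column for the central reader's interpretation.
- Listing 16.2.9.8.2 (local): has an interpretation column, which the central listing lacks.

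Count: 2 of 3 tables are central and 1 is the investigator's. Of the 2 listings, 0 have a column attributed to the central interpretation.

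**Step 2: diagnostic groups.** Protocol 9.6.4 names seven: rhythm, conduction, hypertrophy, arrhythmia, ischemia, infarction, other. They are absent from the SAP 7.5 text, the Appendix F index and every ECG shell, so 0 of 5 outputs show them.

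**Step 3: what the shift table can show.** Table 14.3.4.5.2 crosses three Baseline grades with three grades at each visit, giving 3 × 3 = 9 cells per visit. Two limits follow.

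- A subject graded Abnormal NCS at Baseline who later has a different finding, again graded NCS, falls in the NCS-to-NCS cell. That is the cell for a subject whose ECG did not change, so the new finding leaves no trace in the table. The same holds for CS-to-CS.
- The table is by visit and has no row for any post-Baseline visit. If *a* subjects move from Normal to Abnormal at Week 26 and *b* at Week 52, the number who did so at either visit lies anywhere from max(*a*, *b*) to *a* + *b*. The per-subject count that SAP 7.5 promises cannot be recovered from the table.

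**Step 4: where the information survives.** Listing 16.2.9.8.1 has a free-text description of each abnormality. Protocol 7.1 asks that clinical abnormalities the investigator deems clinically significant be recorded as adverse events, and SAP 7.1 tabulates those by preferred term. A finding judged not clinically significant reaches only the listing.

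**The case against.** Several stronger readings are tempting, and the documents do not support them.

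- A reader might infer that all ECG abnormalities come from the investigator. They do not: rate, intervals and QTc categories are explicitly central.
- A reader might infer that site readings replace the central reader's. The table footnote says only that the investigator determined clinical significance. The listing footnote refers to a central-read CRF, so the investigator may be copying the central wording. The form is not in the documents. What can be said is that no output is attributed to the central interpretation, not that none carries it.
- A reader might infer bias from open-label reading. With one arm and descriptive summaries there is no between-arm comparison to bias. The argument rests on standardisation and agreement with the protocol.
- A reader might infer that the protocol promised incidence tables by type. It says new findings will be categorised, directly after the sentence on listing, and does not say the groups will be tabulated.
- A reader might infer that new findings disappear. Step 4 shows that they do not.

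Two further points are fair. Protocol 7.5 and SAP 7.5 put the overall interpretation in the passive, just after the central-facility sentence, without naming who makes it. Protocol 9.6.4 makes the central reader the natural reading but does not settle it. Also, both documents allow analysis changes to be recorded in the study report, so dropping a descriptive grouping is not improper in itself.

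What stands against these objections is that the only interpretation table is on a different stated basis from Protocol 9.6.4, that the categorisation the protocol does require has no place in the SAP, and that the SAP declares neither.

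**Conclusion.** The point holds for overall, qualitative ECG interpretation and for the diagnostic groups. It does not extend to intervals, rate or QTc.

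Its size is one table of three, the abnormality columns of the central listing, and all seven diagnostic groups, at every scheduled ECG (Baseline, about every 26 weeks, and follow-up). As written, no table gives the number of subjects with a study-emergent qualitative ECG abnormality, overall or by type. How often central and site interpretations differ is not given, so the effect on any reported percentage cannot be stated.

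The conclusion assumes that the central facility supplies an overall interpretation, as Protocol 7.5 and 9.6.4 read together imply, and that the shells will be programmed as drafted. It is partly a conflict between the SAP's own text and its shells, and should be resolved before programming.

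**What to change.** - Base the Normal/Abnormal shift in Table 14.3.4.5.2 on the central reader's interpretation. Show the investigator's CS/NCS call as a separate display.
- Add one table of subjects with any study-emergent centrally read abnormality, overall and by the seven Protocol 9.6.4 groups, with a subject counted once per group. Write the coding rule down, since rhythm and arrhythmia overlap.
- Add a central-interpretation column to Listing 16.2.9.8.1.
- Scheduled triplicate ECGs began with protocol version 3.0, so subjects enrolled earlier may have no centrally read pre-dose ECG. For them, use the first 020 measurement as reference, as SAP 7.5 already does for QTc change, and report them separately, because that reference may itself be on treatment. The footnote of Table 14.3.4.5.3 defines Baseline as pre-dose and should be brought into line with the SAP text.
- If the sponsor prefers the investigator's interpretation or does not want the groups, state and justify the change in SAP Section 9.

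The cost is one extra table, one listing column and the work of coding findings to groups. An overall interpretation is already due for every ECG, so no new data collection is expected.
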